3 TRIAL DESIGN

3.1 General Design and Plan

IPM 032 is a Phase IIIb, multi-centre follow-on open-label trial to evaluate the continued adherence to and safety of the Dapivirine Vaginal Ring-004 inserted at monthly intervals in healthy, HIV-negative women who have participated in the IPM 027 Phase III Dapivirine Vaginal Ring-004 trial. All women who have participated in IPM 027 and are HIV-negative at screening for IPM 032, will be eligible. It was estimated that approximately 1400 participants will be enrolled.

All participants will attend a research centre follow-up visit one month after enrollment. Following this visit, at the investigator's discretion, a participant can continue on a 3-monthly visit schedule. Monthly visits may however be extended up to the first three months of participation. Once the 3-monthly trial visit schedule commences, three rings will be dispensed to the participant. One ring will be self-inserted at the research centre and two additional rings will be dispensed for the participant to take home, or dispensing will take place as arranged with the participant.

Each participant will engage in the screening process for up to 45 days prior to enrollment and will use the Dapivirine Vaginal Ring-004 for a period of up to 12 months. IPM will have the option to extend this trial period. Accrual was expected to take place over approximately 6 months; participants enrolled more than 6 months after the onset of the study site's accrual period may have a shortened follow-up period.

Each participant will have an exit visit 1 to 2 months after ring discontinuation, to assess safety and identify HIV-1 seroconversions after product discontinuation.

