5.2 Modified Intent-to-Treat (m-ITT) Population

Some participants recently infected with HIV-1 may not yet have detectable levels of HIV-1 antibodies at the enrollment visit, and therefore, HIV-infected women who are assumed to be HIV-negative may be enrolled in the trial. To accommodate this situation, an m-ITT population will be determined and used for the analysis of HIV-1 seroconversion rate. This population will exclude all participants who are included in the safety population but who were found to have been HIV-1 infected at the enrollment visit (*i.e.* women who have seroconverted after enrollment but were retrospectively found to be HIV-1 RNA positive at enrollment).

Virology Population

The virology population includes all participants in the m-ITT population, with the exception of those participants who seroconverted after the last product use visit (LPUV). That is, women who were still HIV-1 RNA negative at LPUV, and who became infected after discontinuation of ring use, will be excluded. Genotypic analyses from the small numbers of participants with infection at enrolment, or with no detectable HIV-1 RNA at the LPUV but with seroconversion at the Exit visit, will be described separately.

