- Analysis 3: All confirmed HIV-1 seroconverters determined to have been HIV-1 infected after enrollment will be considered as infected on product, even in instances where HIV-1 seroconversion and estimated point of infection was determined to be after the last product use visit.
- Analysis 4 (HIV-1 infection rate): Similar to Analysis 1, but based on time to first positive HIV-1 RNA.

All additional analyses will be performed on the m-ITT population.

For the number of participants included in the m-ITT analysis in IPM 032, matching placebo participants will be resampled with replacement from the IPM 027 trial, based on research center, age and STI prevalence at screening. These factors were selected because of their strong association with HIV incidence.

Age categories (18-24, and \geq 25 years) will be used to ensure that a sufficient number of participants are represented in each combination of categories of age, center and STI prevalence at screening (Yes/No). This resampling will be repeated 10 000 times; by ordering the 10 000 incidence rates and taking the 250th and 9750th value, a 95% confidence interval can be established. The placebo ring data of the complete double-blind period of IPM 027 will be used for this simulation.

The incidence of HIV-1 seroconversions, the incidence density rate of HIV-1 seroconversion (*i.e.* HIV-1 seroconversion rate per 100 person-years of product use at the end of the ring use period) as well as a 95% confidence interval for the HIV-1 seroconversion rate per 100 person-years (based on the normal approximation of the Poisson distribution) may be presented for the simulated placebo and treatment arm, overall and for each research centre. Similarly, the incidence of HIV-1 seroconversions, the incidence density rate and 95% CI will be presented by visit schedule (A, B or C) and overall. The 95% CI will be calculated using the formula below:

$$95\% \text{ confidence interval} = [(n/PY) \pm 1.96 \times (\sqrt{n/PY} / PY)] \times 100$$

where:

n = number of HIV-1 seroconversions

PY = total number of person-years of product use

Kaplan-Meier curves, of time to HIV-1 seroconversion will be presented, overall and by research centre using PROC LIFETEST in SAS®.

The time to event will be calculated as follows:

Time to event (days) = (Date of seroconversion/Censoring Date – Date of first ring use) + 1

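### The resampled IPM 027 placebo comparator starts its clock at IPM 027 entry, while IPM 032 women are IPM 027 participants selected for still being HIV-negative; the expected incidence may be overstated by an unknown amount

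*SAP*

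**What the plan says.** SAP 9.3.1 states that, for the number of women in the IPM 032 m-ITT analysis, "matching placebo participants will be resampled with replacement from the IPM 027 trial, based on research center, age and STI prevalence at screening". Age has two bands (18-24, and 25 and over), chosen "to ensure that a sufficient number of participants are represented in each combination of categories of age, center and STI prevalence at screening (Yes/No"). The data source is given in one sentence: "The placebo ring data of the complete double-blind period of IPM 027 will be used for this simulation". The procedure is then iterated ("This resampling will be repeated 10 000 times") and the interval read off by "taking the 250th and 9750th value, a 95% confidence interval can be established". The resulting rates "may be presented for the simulated placebo and treatment arm, overall and for each research centre".

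On the IPM 032 side, SAP 3.1 says "All women who have participated in IPM 027 and are HIV-negative at screening for IPM 032, will be eligible". SAP 5.2 adds that the m-ITT population "will exclude all participants who are included in the safety population but who were found to have been HIV-1 infected at the enrollment" visit. Protocol 1.4.2 describes IPM 027 as planned for 24 months of ring use, with 1959 women randomised 2:1 to dapivirine or placebo.

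SAP 9.3.1 does not shift the start of placebo follow-up, require placebo women to be uninfected at a later date, or state the mismatch as a limitation. Analyses 2 to 4 in the same section change how and when IPM 032 infections are counted, not the placebo pool.

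**The concern.** The two rates start from different points. The placebo rate begins when women join IPM 027. The IPM 032 rate begins after those women have already spent time at risk, and only in those who did not seroconvert. Where women in the same stratum differ in risk, those at highest risk tend to be infected first, so the group that remains has a lower average hazard than the group that started. A rate over the whole double-blind period is then too high as the expected rate for the IPM 032 cohort without an active ring.

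IPM 032 has no randomised control (SAP 3.3), so the simulated rate is its only benchmark without an active ring. SAP section 1 says the planned analyses will go into regulatory submissions and/or manuscripts. If the benchmark is too high, part of any gap between it and the observed rate reflects selection, not protection.

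**Working it through.** **1. What can be reproduced.** Expected enrolment: 0.70 × 1959 = 1371.3, against approximately 1400 (difference 2.05%). Percentiles: 250/10 000 = 0.025 and 9750/10 000 = 0.975, which is a 95% interval. Arm sizes at 2:1: 1959/3 = 653 placebo and 1306 dapivirine. The plan states no placebo incidence, expected number of events or effect size for this comparison, so there is no figure of its own to test.

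**2. Model for the selection effect.** Assume that within a matching stratum individual risk follows a gamma distribution with mean 1 and variance θ, around an initial placebo hazard λ. The cumulative population hazard is H(t) = ln(1 + θλt)/θ. Both λ and θ are assumptions. For women from the placebo arm only, compare the mean rate over years 0-2, H(2)/2, with the third-year rate, H(3) − H(2):

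| λ per year | θ | H(2)/2 | H(3) − H(2) | Ratio |
|---|---|---|---|---|
| 0.04 | 1 | ln(1.08)/2 = 0.0385 | ln(1.12/1.08) = 0.0364 | 1.06 |
| 0.06 | 2 | ln(1.24)/4 = 0.0538 | ln(1.36/1.24)/2 = 0.0462 | 1.16 |
| 0.08 | 3 | ln(1.48)/6 = 0.0653 | ln(1.72/1.48)/3 = 0.0501 | 1.30 |

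**3. Allowing for the 2:1 randomisation.** About two thirds of potential entrants came from the dapivirine arm. If the ring lowered their hazard by a fraction e, they carry less prior hazard, 2λ(1 − e) instead of 2λ, and are less depleted. The comparator is events divided by person-years over 24 months on placebo. The target is the same quantity over the next 12 months in women still uninfected, mixing the arms 1/3 and 2/3. With λ = 6 per 100 person-years, θ = 1 and e = 30%, the comparator is 5.67 and the target 5.33 per 100 person-years, an overstatement of 6.4%. A ring with no effect would then appear to cut incidence by 1 − 5.33/5.67 = 6.0%. With e = 0 the overstatement is 8.7%; with e = 50% it is 4.8%.

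Over λ = 3 to 8 per 100 person-years and e = 0 to 50%:

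| θ | Overstatement of expected placebo rate |
|---|---|
| 0 | 0% |
| 1 | 2.4% to 11.4% |
| 2 | 4.7% to 21.7% |
| 4 | 9.1% to 39.4% |

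**4. Calendar trend.** With λ = 5 per 100 person-years, θ = 1 and e = 30%, the overstatement is +5.3% if background incidence is stable, −4.0% if it rises by 10%, and +16.8% if it falls by 10%.

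**5. What a month-12 start would remove.** Replace H(2)/2 by H(2) − H(1) in step 2:

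- λ = 0.04, θ = 1: ln(1.08/1.04) = 0.0377, so the ratio falls from 1.06 to 1.04.
- λ = 0.06, θ = 2: ln(1.24/1.12)/2 = 0.0509, so it falls from 1.16 to 1.10.
- λ = 0.08, θ = 3: ln(1.48/1.24)/3 = 0.0590, so it falls from 1.30 to 1.18.

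On unrounded ratios, that removes about 35%, 38% and 42% of the excess. With the 2:1 mix and e = 30%, the same three cases fall from about +4%, +12% and +23% to about +2%, +6% and +10%, roughly half.

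**The case against.** The strongest case against is that the bias is inferred, not shown. It vanishes if risk is equal within strata. The matching factors were chosen for their association with HIV incidence, so matching takes out part of the risk difference. Prior time at risk is also uncertain: inclusion criterion 1 asks only for previous enrolment in IPM 027, and protocol 4.1 provides for that trial stopping early. Finally, the comparison is optional and supports a secondary endpoint. Protocol 8.4.3.1 contains no placebo comparison, SAP 9.3.1 defines no rate ratio or test against the simulated arm, and the incidence table shells for Analyses 1 to 4 have no column labelled as simulated placebo.

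Most of this stands as a limit on size and importance. It does not remove the mismatch. Equal risk within strata is hard to assume, because SAP 9.3.1 itself lists further potential prognostic factors for the seroconverter profiles (marital status, number of partners, number of sex acts, condom use, anal sex) and matches on none of them. An optional benchmark still needs its limitation stated if it is shown.

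A reader might infer that the fault lies in keeping seroconverters in the placebo pool. It does not. An incidence rate needs its events, and the IPM 027 placebo women were also HIV-negative at entry. Restricting the pool to women who stayed negative, and then using all their follow-up, would set the comparator to zero.

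**Conclusion.** The mismatch of time origin and survivor selection is plain from the documents, and nothing in the SAP addresses it. If risk varies within the centre, age and STI strata, it tends to push the expected placebo incidence upward. Its size cannot be derived from the documents: under the assumptions above it is 0% to about 39%, and 2.4% to 21.7% for θ between 1 and 2.

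Two stronger readings are not supported. A reader might conclude that the comparator does overstate incidence and so flatters the ring. The net direction is not established, because a 10% rise in background incidence reverses the sign in the example, and ageing and who chose to return also matter. A reader might also apply the 6% to 30% range in step 2 to the whole cohort. That range treats every entrant as a former placebo woman with a full 24 months at placebo risk, which neither the 2:1 randomisation nor the entry criteria support.

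**What to change.** Keep the planned resampling. In SAP 9.3.1, specify a delayed-entry sensitivity run of the same 10 000 resamples wherever the simulated rate is presented:

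- Count placebo person-time and events only from month 12 of IPM 027 onward, in women HIV-negative at that point.
- Re-categorise age at month 12. Keep STI at screening unless a later value exists.
- Set a rule in advance for collapsing strata when cells are sparse.
- Report both intervals side by side. State that the landmark removes only part of any survivor bias (about 35-42% in the illustrative model for former placebo women) and that residual selection and calendar trend remain.

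The cost is modest. The data are already held, but the landmark variables must be derived. About half the placebo person-time is dropped, so the interval is wider. Cells also become thinner: six listed centres × 2 age bands × 2 STI levels = 24 cells, and 653/24 is about 27 women per cell before any restriction.

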3.1. Trial Design

IPM 032 is a Phase IIIb, multi-centre follow-on open-label trial to evaluate the continued adherence to and safety of the Dapivirine Vaginal Ring-004, inserted at monthly intervals in healthy, HIV-negative women who have participated in the IPM 027 Phase III Dapivirine Vaginal Ring-004 trial. All women who have participated in IPM 027 and are HIV-negative at screening for IPM 032 will be eligible. An estimate of approximately 1400 participants will be enrolled. All participants will receive the dapivirine vaginal ring containing 25 mg dapivirine (Ring-004) at enrolment and will attend a research centre follow-up visit one month after enrolment. Following this visit, at investigator's discretion, a participant can continue on a 3-monthly visit schedule. Monthly visits may however be extended up to the first three months of participation. Once the 3-monthly trial visit schedule commences, three rings will be dispensed. One ring will be self-inserted at the research centre and two additional rings will be dispensed for the participant to take home, or dispensing will take place as arranged with the participant.

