3.2. Trial Duration

Each participant will engage in the screening process for up to 45 days prior to enrolment and will use the Dapivirine Vaginal Ring-004 for a period of up to 12 months. IPM will have the option to extend this trial period. Accrual will take place over approximately 6 months and those participants who are enrolled more than 6 months after the onset of the study site's accrual period may have a shortened follow-up period.

Each participant will have an exit visit 1-2 months after ring discontinuation, to assess safety and identify HIV seroconversions after product discontinuation.

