In instances where the date of IP initiation, *i.e.* the start date of ring use, is missing or unknown, the missing date will be imputed with the date of the enrollment visit.

In accordance with the protocol, each scheduled visit has a window period of \pm 7 days. If the participant does not return to the research centre for a scheduled visit prior to the start of the trial window of the next visit, the visit will be considered missed. If a participant presents for a visit outside the window for a scheduled trial visit, but prior to the start of the window for the next visit, it will be treated as a late visit. Missed visits and late visits will be documented as protocol deviations (refer to Section 7.2). Data recorded at late visits will be analysed as pertaining to the scheduled visit. Unscheduled visits may be performed at any time during the trial. If an unscheduled visit takes place within any given window period and any repeat observations are made within the given window period, the repeat values will be captured as pertaining to the unscheduled visit. Data from scheduled and unscheduled visits will be shown in the participant listings, and listings will be appropriately labelled when data arise from unscheduled visits. Data from scheduled visits will be presented in the summary tables.

Visit Schedule A will consist of participants who attend Trial Month Visits 1, 4, 7, 10, 13, and 16/Exit; Visit Schedule B will consist of participants who attend Trial Month Visits 1, 2, 5, 8, 11, 14, and 17/Exit; and Visit Schedule C will consist of participants who attend Trial Month Visits 1, 2, 3, 6, 9, 12, and 15/Exit.

Tables, figures, and listings of trial results will accompany the text of the CSR. Listings of all clinical data recorded in the CRFs will be provided, except for those CRFs which are used for administrative purposes, such as the Participant Encounter Form (PEN) and the End of Trial Inventory (ETI). Listings will be sorted by research centre and participant identification number (PID), and key variables such as visit date and/or trial visit number will be presented in each listing.

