9.4 Exploratory Endpoints

9.4.1 Exploratory Endpoint 1: Participant report of feasibility of 3-monthly clinical follow-up schedule

Consistent with exploratory objective 1, exploratory endpoint 1 is the participant report of feasibility regarding a 3-monthly clinical follow-up schedule (Participant Questionnaire).

Assessments

Participants will complete a Participant Questionnaire at all trial visits until the last product use visit. In particular, the following items will be captured:

Participant Questionnaire Part A (month 1, 2 and 3):

Item 1: As per investigator decision are you coming to the research centre next month or in three months for your next visit?

Item 2: Will you take your extra rings with you today or will you come back to the research centre each month to pick up your new ring?

Item 3: What are your reasons for leaving the rings at the research centre today?

Participant Questionnaire Part B (month 2 and 3):

Item 10: If you were not in a study, would you prefer to come to the health care clinic / provider for new rings each month, or every three months?

Item 11: If you were not in a study, would you prefer to come to the health care clinic / provider for an HIV test each month, or every three months?

Participant Questionnaire (3 month follow-up):

Item 1: Will you take your extra rings with you today or will you come back to the research centre each month to pick up your new ring?

Item 2: What are your reasons for leaving the rings at the research centre today?

Item 16: If you were not in a study, would you prefer to come to the health care clinic / provider for new rings each month, or every three months?

Item 17: If you were not in a study, would you prefer to come to the health care clinic / provider for an HIV test each month, or every three months?

Participant Questionnaire (last product use visit):

Item 1: When you were doing your three monthly visits, did you take your extra rings with you or did you come back to the research centre each month to pick up your new ring?

Item 2: What were your reasons for leaving the rings at the research centre?

Item 16: If you were not in a study, would you prefer to come to the health care clinic / provider for new rings each month, or every three months?

Item 17: If you were not in a study, would you prefer to come to the health care clinic / provider for an HIV test each month, or every three months?

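### HIV-1 incidence by visit schedule A/B/C counts person-time from before the schedule is known, so with no true difference C can appear about 10% below A

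*SAP*

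**What the plan says.** **The analysis.** In SAP 9.3.1, "the incidence density rate and 95% CI will be presented by visit schedule (A, B or C) and overall". This is a firm commitment; the neighbouring sentence on the simulated placebo display is only permissive.

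**The groups.** SAP 6.6 defines them by attendance. The first definition reads: "Visit Schedule A will consist of participants who attend Trial Month Visits 1, 4, 7, 10, 13, and 16/Exit". The second has one extra monthly visit before the 3-monthly rhythm begins: "Visit Schedule B will consist of participants who attend Trial Month Visits 1, 2, 5, 8, 11, 14, and 17/Exit". The third has two extra monthly visits: "Visit Schedule C will consist of participants who attend Trial Month Visits 1, 2, 3, 6, 9, 12, and 15/Exit".

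**How a woman gets her schedule.** It is neither randomised nor fixed at enrolment. Everyone attends at Month 1. SAP 3.1 continues: "Following this visit, at the investigator's discretion, a participant can continue on a 3-monthly visit schedule". Protocol 3.1 says the same and lets monthly visits run to at most the third month. SAP 9.4.1 lists a Month 1 to 3 questionnaire item that records the choice: "As per investigator decision are you coming to the research centre next month or in three months for your next visit". The SAP does not say that this item assigns the schedule.

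**Person-time.** SAP 9.3.1 measures time to event from first ring use. The shells for Tables 14.3.7.5 to 14.3.7.8 compute person-years from first ring insertion to last ring removal.

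**Seroconverters.** Protocol 5.4.3 withholds the ring and moves to last-product-use procedures when the rapid tests are reactive, and takes confirmed cases permanently off product and trial.

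**Unassigned women.** The disposition shell (Table 14.1.1.1) has an Unknown schedule column. Listing 16.2.1.1 shows only A, B or C. The incidence shells are laid out by IPM 027 arm and have no schedule columns.

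**The concern.** Group membership depends on what happens after the clock starts. To be recognisable as A rather than B or C, a woman must get past Month 1 still on product. To be told apart as B or C, she must get past Month 2. Women who manage this bring those early months into their schedule's denominator. Women who seroconvert in those months have no single schedule to be counted in. This is immortal time: denominator with no matching opportunity for an event. Because the amount differs (1 month against 2), the distortion does not cancel between schedules.

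At stake is a set of adjacent rates with confidence intervals that readers will compare. A longer monthly phase could look mildly protective purely from the way the table is built. The same undefined grouping is used for the resistance results (SAP 9.3.2) and disposition (SAP 7.1).

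**Working it through.** The plan states no figure on this point, so there is nothing of its own to reproduce.

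**Inputs**
- Months that must be event-free before a woman can be classified (f), from the visit patterns in SAP 6.6: A = 1, B = 2, C = 2. C is 2 rather than 3 because a woman who attends Months 1, 2 and 3 and tests positive at Month 3 fits only C.
- Months of person-time from first insertion (T): A = 13, C = 12 if the last visit before Exit in SAP 6.6 ends product use; 12 for both under the protocol's limit of up to 12 months; 16 and 15 if the months marked Exit are taken as the end of use.
- Assumptions: constant hazard, equal across schedules; early seroconverters left unassigned. The documents give no incidence for this trial, so 1 to 5 per 100 person-years was used.

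**Formula.** Reported rate / true rate = (T − f) / T.

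| f, T for A | f, T for C | A / true | C / true | C / A | C below A |
|---|---|---|---|---|---|
| 1, 13 | 2, 12 | 12/13 = 0.923 | 10/12 = 0.833 | 0.903 | 9.7% |
| 1, 12 | 2, 12 | 11/12 = 0.917 | 10/12 = 0.833 | 0.909 | 9.1% |
| 1, 16 | 2, 15 | 15/16 = 0.938 | 13/15 = 0.867 | 0.924 | 7.6% |
| 1, 13 | 3, 12 | 12/13 = 0.923 | 9/12 = 0.750 | 0.813 | 18.8% |
| 1, 12 | 3, 12 | 11/12 = 0.917 | 9/12 = 0.750 | 0.818 | 18.2% |
| 1, 16 | 3, 15 | 15/16 = 0.938 | 12/15 = 0.800 | 0.853 | 14.7% |

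The last three rows apply only if the assignment rule required C women to be negative at Month 3.

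For B against A with T = 13: 12/14 = 0.857 gives 7.1% lower if B's product use ends at Month 14, and 9/11 = 0.818 gives 11.4% lower if it ends at Month 11.

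**Visit-based check.** An exponential model with events dated at visits, run at 1, 2, 3 and 5 per 100 person-years, puts C 9.7% to 9.8% below A with 2 event-free months, and 18.8% to 18.9% below with 3. At a true 2.0, A reports 1.840 and C 1.661. With nobody excluded the values are 1.995 and 1.996, so each schedule falls below the overall rate.

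**Other allocation rules.** If every early seroconverter goes to her intended schedule, the gap is 0%. If all Month 1 seroconverters defaulted to A, with one third of women per schedule, A = (1/3 × 2.0 × 12/12 + 2.0 × 1/12) / (1/3 × 13/12) = 2.31. C at 10/12 × 2.0 = 1.67 is then 28% lower.

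**After the fix.** With person-time started at the visit where the schedule becomes known, A, B and C all report 1.995 at a true 2.0.

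**Precision.** With 1400 women split equally, one year each and 2 per 100 person-years, a schedule has 466.7 × 0.02 = 9.3 expected events. C keeps 9.3 × 10/12 = 7.8 (7.0 with 3 months lost). The relative 95% half-width is 1.96/√7.8 = 70% (74% at 7.0 events). The events missing from C number 9.3 × 2/12 = 1.6.

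**The case against.** The strongest reply is that the SAP states no assignment rule, so the bias is possible rather than built in. Listing 16.2.1.1 foresees a schedule for each enrolled woman, the investigator's decision is recorded, and allocation by intended schedule would remove the gap. It stands that the documents do not fix the outcome. But an intended schedule is unlikely to exist for a woman who tests positive at Month 1, because her visit turns into last-product-use procedures. The Unknown column also shows that some women were expected to have no schedule.

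It also stands that the display is descriptive, that sampling error is far larger than a 10% shift, and that investigators choose the schedule, so the groups would differ by selection even with the clock corrected. A confidence interval does not cover a systematic shift, however, and this one is cheap to remove.

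Three stronger readings are tempting and not supported:
- A reader might infer that C loses 3 months and sits 19% below A. That needs C women to be negative at Month 3, which the attendance patterns do not require.
- A reader might infer that these rates decide whether 3-monthly follow-up is feasible. Protocol 2.2 and SAP 9.4.1 assess feasibility through questionnaire answers, women declining the extra rings and ring returns; incidence is not listed.
- A reader might take attendance literally and conclude that only women who complete every visit count. The disposition shell tabulates discontinuation for seroconversion within each schedule, which points the other way.

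**Conclusion.** The point holds for the by-schedule breakdown. As written, the rates for A, B and C are open to a downward bias of unequal size: with early seroconverters unassigned, about 8% for A (1/13) and 17% for C (2/12). The central estimate of C against A is a 10% deficit where the truth is none. This rests on a constant, equal hazard and on no allocation rule being applied; the relative size hardly depends on the incidence assumed. The overall rate and its interval are untouched, so nothing here weakens the secondary endpoint itself. It is nonetheless more than a missing detail, because the SAP commits to the analysis and a change of start date removes the bias.

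A separate point concerns the visit months. SAP 6.6 ends the schedules at Months 13 then 16/Exit, 14 then 17/Exit and 12 then 15/Exit. Protocol Appendix A has the last product use visit at Month 12 and the exit visit at Months 13 to 14, and Protocol 3.2 says: "Each participant will have an exit visit 1-2 months after ring discontinuation". The sponsor may extend the trial period, so this calls for reconciliation and does not bear on the bias, beyond widening the range of T.

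**What to change.** 1. State in SAP 6.6 that the schedule is assigned from the investigator decision recorded at the Month 1, 2 or 3 visit (Questionnaire Part A, item 1).
2. In the by-schedule incidence display, count events and person-years only from the visit at which 3-monthly follow-up starts.
3. Put all earlier time and events, and women never assigned, in a separate monthly-phase/Unknown row, so that the rows add up to the overall rate.
4. Label the display descriptive and non-randomised.
5. Use the same assignment in the resistance and disposition tables.
6. Reconcile the final visit months in SAP 6.6 with the protocol.

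The cost is SAP wording, a shell for the by-schedule incidence display (the current incidence shells have no schedule columns), edits to a few other tables, and slightly fewer person-years per schedule. No new data are needed.
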